3.1.6.1 Study Discontinuation

3.1.6.1.1 Study discontinuation criteria

When a patient meets any of the following criteria, the Principal Investigator or a Sub-Investigator will discontinue the patient from the study.

- a. The patient requests withdrawal from the clinical study
- b. The patient died
- c. The patient is lost to follow-up
- d. The patient is otherwise deemed ineligible to continue in the study by the Principal Investigator or a Sub-Investigator (e.g adverse event or pregnancy)
- e. Upon request by the CRO or Sponsor Medical Monitor (with appropriate justification)

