If patient is discharged from the hospital before Day 28, the assessments mentioned in the end of study visit (Day 28) will be performed before the patient is discharged. After discharge, telephonic follow up will be performed on Day 10 (applicable only for patients who are discharged earlier than Day 10 and if patients are unable to visit the site for EOT on Day 10), Day 14, Day 21 and Day 28. The telephonic follow up will be as applicable for the individual patient, depending upon the actual day when (s)he is discharged. A 2-day window period is allowed for telephonic follow up.

In case the patient remains admitted in the hospital beyond Study Day 28, the end of study assessments will be performed for the patient on Day 28 (+2) days.

Stage I of the study will be completed when the 'Day 28' assessment is completed either as an in-patient assessment if the patient is still hospitalized, or as a telephonic follow up assessment if the patients are discharged earlier to Day 28.

Once all the patients complete the Stage I of the study, the database would be locked, and analysis will be performed.

Stage II – Extended Follow Up:

[figure not shown]
Statistical Analysis Plan
Sponsor: [name] Ltd.

Study Number: NV-05-983-2020

Version: 2.0 Date: 06JAN2021

All the patients will be followed up for AEs or for 'clinical relapse' of COVID 19. Two telephonic follow up assessments will be performed on Day 42 and Day 60. An additional visit to the hospital (for further assessment) may be scheduled for such patients, if required. A 2-day window period is allowed for telephonic follow up.

The below flowchart will describe about the study design.

* If patient is discharged from the hospital before Day 28, a telephonic follow up will be performed on Day 10 (applicable only for patients who are discharged earlier than Day 10 and if patients are unable to visit the site for EOT on Day 10), Day 14, Day 21 and Day 28 as applicable for the individual patient.

	Statistical Analysis Plan Sponsor: [name], Inc	
	Study Number: NV-05-983-2020	Version: 2.0 Date: 06JAN2021

The schedule of assessments will be as follows:

Table 1: Study Assessment Schedule

Assessments	STAGE I – Main Study ¹												Database Lock	Stage II – Extended Follow Up ²		Unscheduled Visit
	Screening ³	Randomization (Baseline) ⁴					EOT ⁵			End of Study						
Day	-3 to -1 (72 hrs)	1 (Pre-dose)	1 (Post-dose)	On all days until discharge	On all days until Day 10	4	5	7	10	14	21	28 or discharge		42	60	

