9.2 Analysis Population

Four analysis populations will be considered as defined below:

Analysis Population	Definition
Screened Population	All participants who signed the informed consent form
Safety Population (SAF)	All randomized patients who received at least one dose of the study medication
Intention-to-treat (ITT)	All randomized patients who received at least one dose of the study medication
Modified Intention to treat (mITT)	All randomized patients who received at least one dose of the study medication and has at least one post dose primary efficacy endpoint assessment available. (Note: if there is a greater than 5% difference in the number of patients in the ITT and mITT populations, then analysis for mITT population will be provided additionally.)
Per protocol set (PPS)	All patients included in the ITT who complete the study without major protocol deviation which would affect the primary endpoint of the study.

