Necessary steps will be taken to properly manage the situation of informative censoring for patients who did not reach the resolution of hypoxia endpoint. For censored patients who died of any cause, discontinued or were lost to follow-up due to treatment-related adverse events or lack of efficacy, they will be censored at Day 28. However, censored patients who discontinued or were lost to follow-up for reasons that were independent of the study medication will be censored at the day of discontinuation of lost to follow-up. Censored patients who were still in the study follow-up at the time of the analysis will be censored at the last day of available follow-up data.

The above primary endpoint analysis will be done using ITT population

Also, the primary efficacy analysis will be repeated using PP population.

Sensitivity analysis for primary endpoint [12](#):

Three sensitivity analyses are planned.

1. The first is a more relaxed definition of time to resolution of hypoxia. In this analysis, the resolution of hypoxia is defined if subject's clinical status score ≤ 4 is maintained for two consecutive days. The timing of the resolution event will still be the first day when the score falls to 4 or lower. This sensitivity analysis will be done using ITT as described in the primary endpoint.

Statistical Analysis Plan
Sponsor: [name], Inc

Study Number: NV-05-983-2020

Version: 2.0 Date: 06JAN2021

2. The second sensitivity analysis will be based on Kaplan-Meier estimates and log-rank test. Median time to event, along with standard error, percentage of patients achieved resolution of hypoxia, percentage of patients censored, and two-sided p-value obtained using log-rank test at 5% level of significance will be presented for observed case using ITT population.
3. The third sensitivity analysis will be a worst-rank analysis proposed by Lachin (1999). The two treatment groups will be compared by a Wilcoxon-Mann-Whitney test as implemented in SAS PROC NPAR1WAY. Tied ranks will be assigned the midrank. The ranks will be determined as follows:
 - 1) The lowest (best) ranks will be given to patients who meet the primary endpoint definition of treatment success, beginning with the earliest treatment success after beginning of treatment, and survive to Day 28.

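### The per-protocol set requires study completion, so the supportive per-protocol repeat of the primary analysis drops patients who die before Day 28 and selects on part of its own outcome

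*SAP*

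**What the plan says.** SAP 9.2 defines the per-protocol set as "All patients included in the ITT who complete the study without major protocol deviation" that would affect the primary endpoint, and Protocol 11.1 uses the same words. Completion and freedom from major deviation are two separate conditions.

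Protocol 3.1.6.1.1 sets the rule for leaving the study: "When a patient meets any of the following criteria, the Principal Investigator or a Sub-Investigator will discontinue the patient from the study". Item b on that list is "The patient died". Item d covers patients judged ineligible to continue, with adverse event as an example. On completion, SAP 8.1.1 (and Protocol 3.1.1) says: "Stage I of the study will be completed when the 'Day 28' assessment is completed", either in hospital or by telephone.

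For the primary endpoint, SAP 10.6.1 says: "The above primary endpoint analysis will be done using ITT population", and then: "Also, the primary efficacy analysis will be repeated using PP population". Component (c) of the endpoint requires the patient to have survived without COVID-19 readmission through Day 28. The same section has a rule against informative censoring. It begins "For censored patients who died of any cause, discontinued or were lost to follow-up due to treatment-related adverse events or lack of efficacy" and censors these patients at Day 28. Those who leave for reasons unrelated to study medication are censored on the day they leave.

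**The concern.** A per-protocol set is meant to remove departures from the protocol. SAP 9.4 gives the kinds it has in mind: eligibility breaches, forbidden medication and non-compliance. Death is none of these. It is an outcome, and here it is part of the primary endpoint. A set that requires completion conditions on survival after randomization, so the two groups being compared are survivors of each arm.

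It also disables the SAP's own safeguard. The rule that holds deaths in the risk set to Day 28 has no deaths to act on in the per-protocol run. If the ITT and per-protocol hazard ratios then differ, the reader cannot tell whether adherence or the removal of deaths caused it.

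**Working it through.** **Chain of text.** (1) The set requires completion (SAP 9.2, Protocol 11.1). (2) A patient who dies is discontinued from the study (Protocol 3.1.6.1.1, item b). (3) Stage I is complete only at the Day 28 assessment (SAP 8.1.1). (4) SAP 10.1 likewise separates patients who completed according to the protocol from those who discontinued prematurely. A patient who dies before the Day 28 assessment is therefore outside the set, and no passage readmits that patient.

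**The plan's design figures (SAP 9.6), used to scale the check.** Events = 4(1.960 + 0.842)² / (ln 1.25)² = 31.40 / 0.0498 = 630.5, so 631 as stated. 631 / 0.85 = 742.4, or 371 per group. Dropout of 5% gives 371 × 1.05 = 389.6, the stated 390; dividing by 0.95 gives 391. The design figures reproduce.

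**Inputs to the check.** From the plan: 390 per group, 28 days, 0.80 of control patients resolving, hazard ratio 1.25. Assumed, because the documents give no figure: Day 28 mortality of 5% to 20%. Also assumed: exponential resolution times counted in whole days, death independent of resolution time, and a Cox model with treatment only.

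**Direction by hand, 10% placebo v 15% drug deaths, no effect among survivors.** Resolution among survivors is 0.80 / 0.90 = 0.889 in both arms. With deaths kept, 0.800 v 0.889 × 0.85 = 0.756 resolve. With deaths dropped, 0.889 v 0.889. The difference vanishes.

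**Hazard ratios by simulation.** Deaths are either kept as non-events to Day 28 (the ITT rule) or dropped (the per-protocol set as written).

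| Deaths, placebo v drug | HR among survivors | HR, deaths kept | HR, deaths dropped |
|---|---|---|---|
| 5% v 5% | 1.00 | 1.00 | 1.00 |
| 5% v 7.5% | 1.00 | 0.95 | 1.00 |
| 5% v 10% | 1.00 | 0.90 | 1.00 |
| 10% v 15% | 1.00 | 0.90 | 1.00 |
| 10% v 20% | 1.00 | 0.81 | 1.00 |
| 10% v 5% | 1.00 | 1.12 | 1.00 |
| 5% v 10% | 1.25 | 1.08 | 1.24 |
| 10% v 20% | 1.25 | 0.93 | 1.24 |
| 10% v 5% | 1.25 | 1.34 | 1.24 |

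A variant of the 10% v 15% case, with median resolution of 7 days, gives 0.89 kept and 0.99 dropped.

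With hazard ratio 1.25 among survivors and deaths 5% v 10%, the chance of a significant benefit (z above 1.96, 390 per group, 1,000 runs) is 14% with deaths kept and 77% with deaths dropped. At 10% v 5% it is 97% and 79%. At 5% v 10% the set loses about 20 placebo and 39 drug patients of 390 each.

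**The case against.** The strongest reply is that this is a supportive repeat that decides nothing. The primary test is in ITT. The interim efficacy boundary, futility rule and sample size reassessment in SAP Appendix I do not refer to the per-protocol set. Deaths are kept in the ITT Cox model, take the worst ranks in the third sensitivity analysis, are tested as secondary endpoint 15 in ITT, appear in the safety tables, and are compared for the DMC at the interim. This stands. A reader might infer that the trial could hide a mortality harm; the documents do not support that.

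The planned mortality comparison would usually show such harm better than the primary analysis. At 10% v 15%, its expected z is 0.05 / √(0.125 × 0.875 × 2/390) = 0.05 / 0.0237 = 2.1. The Cox model with deaths kept has about 390 × (0.800 + 0.756) = 607 events, standard error 2/√607 = 0.081, and expected z of ln(0.901) / 0.081 = −1.3. Often there would be no significant ITT signal to lose.

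Three other strong readings also fail:

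- **Every withdrawal for an adverse event or lack of efficacy is excluded.** Protocol 3.1.6.2.2 encourages patients who stop study drug to stay for assessments, so stopping drug does not end completion. Only withdrawal from the study does, and lack of efficacy is not a listed criterion in 3.1.6.1.1.
- **Every death is excluded.** This is certain only before the Day 28 assessment. The definition does not say whether completion means Stage I or Day 60, so later deaths are unclear.
- **A drug that raises mortality always looks neutral in the per-protocol set.** The value of 1.00 follows from assuming no effect among survivors. If the drug also slowed recovery, the set would show that part.

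A completers set is a familiar convention, but convention does not answer the point. Here completion includes survival, and survival is in the endpoint.

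**Conclusion.** The definition is wrong as written for the analysis it serves. The per-protocol repeat omits all deaths before the Day 28 assessment, and also patients withdrawn from the study for adverse events, and so selects on its own outcome. With no effect among survivors, true hazard ratios from 0.81 to 1.12 all read as 1.00 across the assumed death rates; at 5% v 7.5% the gap is only 0.95 v 1.00. With equal mortality of 5%, the two agree when there is no effect and differ little at hazard ratio 1.25 (1.22 kept, 1.24 dropped). The distortion can conceal either excess deaths or lives saved.

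The textual finding does not depend on the simulation. The sizes do: they rest on assumed mortality, exponential resolution times, death independent of resolution time, and no covariates. This is a defect in a supportive analysis, worth correcting because that analysis is the only planned per-protocol support for the primary result.

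**What to change.** In SAP 9.2 and Protocol 11.1, remove the completion condition. Define the per-protocol set as ITT patients without a major protocol deviation affecting the primary endpoint, with deviations classified before unblinding in the data review that SAP 9.4 already requires before database closure. Then state three things:

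- Death and informative study withdrawal are not deviations.
- Both stay in the set under the Day 28 rule of SAP 10.6.1.
- Withdrawals and losses unrelated to treatment are also kept and are censored on the day they leave, as in the ITT analysis.

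This also removes the doubt over Day 28 or Day 60, which matters because SAP 12 requires population assignment to be agreed before each database lock.

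The cost is a wording amendment to the SAP and protocol, with ethics committee submission under Protocol 12.8, and a set that no longer consists of completers. No new data are needed.

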9.3 Definitions

In the following table, the definitions and calculation of derived variables are summarized

Variable / Term	Definition / Way of calculation
Age	Int ((informed consent date – Birth date +1)/365.25)
Baseline	The last valid value prior to the first dose of study treatment
Treatment Start Date	Date of dose administration on Day 1

Statistical Analysis Plan
Sponsor: [name], Inc

Study Number: NV-05-983-2020

Version: 2.0 Date: 06JAN2021

Variable / Term	Definition / Way of calculation
Treatment End Date	Date of Last Study Medication Taken
Duration of exposure	Treatment end date- Date of randomization + 1
Treatment Emergent AE (TEAE)	An AE will be considered as treatment-emergent if the time of onset is on or after the time of the first study drug administration or any AE that exist prior to first dose and its severity increased during the study.
Time to Resolution of Hypoxia	Date of first time the status trial score to become 4 or lower following baseline assessment when evaluated over a period of 24 hours – Date of randomization +1
Time to discharge	Date of discharge – date of randomization + 1
Time to ALL COVID-19 associated symptoms to become '0=absent' or 'mild =1' from Randomization	Earliest Date of ALL COVID-19 associated symptoms to become either '0=absent' or 'mild =1' in assessments over a period of 24 hours – date of randomization + 1
Time to achieve symptom improvement	Date of Change from baseline value for the particular symptom score to become less than or equal to '-1' and sustained at evaluations over a period of 24 hours – Date of randomization +1
Time to Negative	Date of first time to negative conversion in RT-PCR – Date of randomization + 1

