8.2 Efficacy endpoints

Stage I

Primary Efficacy Endpoint:

Time to resolution of hypoxia (Time frame: Up to 28 days)

This endpoint will be considered to have been met when the patient has attained a score of 4 or lower on the 10-point ordinal scale of clinical status and either of a) or b), and c) is met:

- a) Score is ≤ 4 on consecutive assessments over the next 5 days, if patient continues to remain in hospital (i.e., has not been discharged).

OR

- b) Patient was discharged before five consecutive assessments (after reaching a score of 4).

AND

- c) The patient has survived and has not been re-admitted to hospital for COVID-19 management through Day 28.

*Note: Part c) is applicable to patients in both a) and b)
 i.e. Time to resolution of Hypoxia = either "a and c" OR "b and c" is met.*

Secondary Efficacy Endpoints:

1. Time to discharge from hospital.
2. Time (no. of days) from randomization to the earliest time when **ALL** COVID-19 associated symptoms (fever, chills, cough, sore throat, malaise, headache, muscle pain, gastrointestinal symptoms – specifically diarrhoea and vomiting, shortness of breath or dyspnoea) are scored by the Investigator/trained study personnel as either '0=absent' or 'mild=1' in assessments over a period of 24 hours, when assessed from baseline to Day 28 or discharge from hospital (if discharge happens earlier than Day 28).

Statistical Analysis Plan
Sponsor: [name], Inc

Study Number: NV-05-983-2020

Version: 2.0 Date: 06JAN2021

3. Percentage of patients with score of either '0=absent' or 'mild =1' over a period of 24 hours, for **ALL** COVID-19 associated symptoms, by Days 4, 7, 10 14, 21 and 28 or discharge (if discharge happens earlier than one or more of the above-mentioned time points)

Note: Symptoms evaluated are fever, chills, cough, sore throat, malaise, headache, muscle pain, gastrointestinal symptoms- specifically, diarrhoea and vomiting, shortness of breath or dyspnoea. The Investigator/trained study personnel will assess (including by enquiry with the patient, as necessary) and score the severity of each COVID-19 associated symptom on a 5 point Likert-type scale (0= absent, 1= mild, 2=moderate, 3= severe, 4= very severe/critical).

4. Time to improvement in **EACH** of the symptoms of fever, chills, cough, sore throat, malaise, headache, muscle pain, gastrointestinal symptoms- specifically diarrhoea and vomiting, shortness of breath or dyspnoea by at least 1 grade over baseline.

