9.5 Data Handling

9.5.1 Imputation of Missing data

Efficacy: As the patients were in the hospital until discharge, missing data in the daily WHO clinical status scores were few. To facilitate the definition of the durable response as part of the primary efficacy endpoint which now requires five consecutive days of clinical status score at 4 or lower, a very limited and conservative imputation will be implemented to impute a missing clinical status score if adjacent to a valid score on both sides, the imputed score will be the higher (worse) of the two. For example, if Day 10 score is missing with Day 9 score of 5 and Day 11 score of 4, then the imputed Day 10 score will be 5.

Safety: To handle missing or partial AE and concomitant medication date, the following rules will be applied.

For partial start dates:

1. If the year is unknown, then do not impute the date but assign a missing value.
2. If the month is unknown, then:
 - a. If the year matches the year of the dose date, then impute the month and day of the dose date.
3. If the day is unknown, then:
 - a. If the month and year match the month and year of the first dose date, then impute the day of the dose date.
 - b. otherwise, assign "01"

For partial end dates:

1. If the year is unknown, then do not impute the date but assign a missing value.
2. If the month is unknown, then do not impute the date and mark as ongoing for AE and Concomitant medication.
3. If month is known but the day is unknown, then assign the last day of the month.

After implementing the rules above, to determine whether AEs (or medications) with missing start or stop dates are pretreatment or on/after treatment, the following strategy will be used:

1. If the start date and stop date are both missing, then the most conservative approach is taken and the AE (or medication) is considered to be treatment emergent (or concomitant medication).
2. If the start date is missing but the stop date is not missing and is on or after the day of study dose administration, then the most conservative approach is taken and the AE (or medication) is considered to be treatment emergent (or concomitant medication).

Statistical Analysis Plan
Sponsor: [name], Inc

Study Number: NV-05-983-2020

Version: 2.0 Date: 06JAN2021

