10.6 Efficacy Analysis

10.6.1 Primary Efficacy endpoint

Primary Efficacy endpoint will be as follows:

1. Time to resolution of hypoxia

The primary efficacy endpoint is “Time to resolution of hypoxia (Time frame: Up to 28 days)”

This endpoint will be considered to have been met when the patient has attained a score of 4 or lower on the 10-point ordinal scale of clinical status and either of a) or b), (as applicable) and c) is met:

- a) Score is ≤ 4 on consecutive assessments over the next 5 days, if patient continues to remain in hospital (i.e., has not been discharged).

OR

Statistical Analysis Plan
Sponsor: [name], Inc

Study Number: NV-05-983-2020

Version: 2.0 Date: 06JAN2021

- b) Patient was discharged before five consecutive assessments (after reaching a score of 4)

AND

- c) The patient has survived and has not been re-admitted to hospital for COVID-19 management through Day 28.

*Note: Part c) is applicable to patients in both a) and b).
 i.e. Time to resolution of Hypoxia = either "a and c" OR "b and c" is met.*

Time to resolution of hypoxia will be compared between the treatment groups using the Cox proportional hazard model with age, gender, and baseline score on the 10-point ordinal scale of clinical status as covariates. The hazard ratio and its corresponding two-sided 95% confidence interval (CI) and two-sided p -value at 5% level of significance will be obtained from the above Cox proportional hazard model.

As the patients were in the hospital until discharge, missing data in the daily WHO clinical status score were few. To facilitate the definition of the durable response, a very limited and conservative imputation will be implemented to impute a missing clinical status score if adjacent to a valid score on both sides, the imputed score will be the higher (worse) of the two, as discussed in Section 9.5.1.

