Appendix I: Interim Analysis Plan

A single unblinded interim analysis of the primary efficacy endpoint, that is, time to resolution of hypoxia, will be conducted. Resolution of hypoxia is defined as described in Section 10.6.1. This endpoint will be considered to have been met when the patient had attained a score of 4 or lower on the 10-point ordinal scale of clinical status used by the WHO in the SOLIDARITY trial, and either maintained the score of 4 or lower for five consecutive assessments over 5 days or was discharged after reaching the score of 4 or lower. In addition, the patient must also survive and not be readmitted to hospital due to COVID-19 related complications through Day 28 to be considered meeting the endpoint. To be performed when data for time to resolution of hypoxia become available for either the first 390 randomized subjects (50% of the target enrollment) or subjects enrolled by the end of year 2020, whichever is earlier, interim analysis will be conducted for three purposes: 1) Possible early stopping for demonstrated efficacy of the study treatment, 2) Possible early stopping for futility (lack of efficacy), and 3) Sample size reassessment. After reviewing the analysis, the DMC will make a recommendation concerning continuation of the study as planned, termination, or continuation with a larger sample size.

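### SAP 9.3 derives the primary time variable with a 24-hour rule that conflicts with the five-day, discharge and Day 28 conditions defining the endpoint in SAP 10.6.1

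*SAP*

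**What the plan says.** SAP 9.3 opens by saying that in its table "the definitions and calculation of derived variables are summarized". The row for time to resolution of hypoxia takes the "Date of first time the status trial score to become 4 or lower following baseline assessment when evaluated over a period of 24 hours" and subtracts the date of randomization, plus 1. The row says nothing more and does not refer to another section.

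SAP 8.2 and 10.6.1 define the same variable in three parts, once the score has reached 4 or lower:

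- (a) it remains there "on consecutive assessments over the next 5 days, if patient continues to remain in hospital"; or
- (b) "Patient was discharged before five consecutive assessments (after reaching a score of 4"; and
- (c) the patient survives and is not readmitted for COVID-19 through Day 28. SAP 8.2 adds that "Part c) is applicable to patients in both a) and b".

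Protocol 3.1.3.1.1 and 7.1.1.1 give the same three parts. SAP 9.5.1 describes the endpoint as one "which now requires five consecutive days of clinical status score at 4 or lower". Appendix I, for the interim analysis, states "Resolution of hypoxia is defined as described in Section 10.6.1". Among the sensitivity analyses in 10.6.1, a rule of two consecutive days is introduced with the words "The first is a more relaxed definition of time to resolution of hypoxia".

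**The concern.** A programmer who needs a formula for the primary time will find only one, in 9.3, and it describes a different endpoint. Its persistence rule is 24 hours instead of five days. It has no discharge route and no Day 28 condition. With once-daily scoring (Protocol 6.3.1.3), 24 hours means one or two daily scores, so the row is no stricter than the two-day rule that 10.6.1 reserves for a sensitivity analysis.

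Programming the row would have three effects on the confirmatory analysis:

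- Patients who improve briefly, die later or are readmitted would become events.
- A patient who lapses and later responds durably would be dated from the earlier, failed run.
- If 24 hours is taken to need two daily scores, a patient discharged on the first day at 4 or lower would be lost as an event, although (b) and (c) count that patient.

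The interim analysis is tied explicitly to 10.6.1, so a final analysis programmed from 9.3 would also test a different endpoint from the one behind the stopping and sample-size decisions.

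**Working it through.** **Planned size.** The inputs are in SAP 9.6: hazard ratio 1.25, significance level 0.05 (two-sided in 10.6.1), power 80%, 1:1 allocation, event probabilities 0.9 and 0.8, and dropout 5%.

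- Events = 4 × (1.960 + 0.842)² / (ln 1.25)² = 630.5, so 631 as stated.
- Patients = 630.5 / 0.85 = 741.8, so 742, or 371 per group.
- Randomized = 371 × 1.05 = 389.55, so 390 per group and 780 in total.

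The plan's figures reproduce. None of the stated inputs depends on the 9.3 row.

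**The two rules compared.**

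| Element | SAP 9.3 row | SAP 8.2 and 10.6.1 |
|---|---|---|
| Persistence in hospital | 24 hours | five days |
| Discharge route | none | (b) |
| Alive, not readmitted, to Day 28 | not required | (c), for both routes |
| Event date | first score of 4 or lower | the score that starts the run (implied by part a) |

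**Worked cases.** These are invented daily scores that show where the rules part. They do not estimate frequency. The 9.3 row was read with 24 hours as one and as two daily scores. Rule 10.6.1 was read with a run of five scores and with the first score plus five more. Results are the same under all readings unless noted.

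| Case | Course | 9.3 | 10.6.1 |
|---|---|---|---|
| 1 | 4 or lower on Days 6-7, 5 on Days 8-11, 4 or lower on Days 12-18, discharged Day 18 | Day 6 | Day 12 |
| 2 | 4 or lower on Days 5-6, then 6, dies Day 20 | event, Day 5 | no event, censored Day 28 |
| 3 | 4 or lower on Days 4-9, then worsens and dies before Day 28 | event, Day 4 | no event, censored Day 28 |
| 4 | 4 or lower on Days 9-10, discharged Day 10, readmitted for COVID-19 Day 15 | event, Day 9 | no event |
| 5 | 4 or lower on Days 7-8 only, in hospital to Day 28 | event, Day 7 | no event |
| 6 | first 4 or lower on Day 9, discharged that day, alive and not readmitted | Day 9 with one score; no event with two | event, Day 9 |
| 7 | 4 or lower on Days 10-16, discharged Day 16 | Day 10 | Day 10 |
| 8 | 4 or lower on Days 8-12, then 5, in hospital | event, Day 8 | Day 8 with five scores; no event with first plus five |

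Case 1 is dated 12 − 6 = 6 days early. Case 3 isolates condition (c), because the five-day run is complete before the patient dies. Case 7 shows the rules agree for a patient who reaches 4 or lower and holds it. Case 8 concerns run length only: part (a) can be read as the first score plus five more, while part (b), 9.5.1 and Appendix I speak of five.

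**Does any text settle the conflict?** The precedence clause (Protocol 3.1.2 and 11.4.2) ranks the SAP over the protocol, so the protocol's definition does not correct a SAP row. No clause ranks 9.3 against 10.6.1. SAP 11 declares no deviation from the protocol, which suggests the row was not meant as a change.

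**The case against.** The best defence is that 9.3 only summarizes date arithmetic, and 10.6.1 decides who has the event. Other rows in the table, such as time to discharge, also leave their censoring rules to 10.6.2. The first sensitivity analysis says the event will still be timed at the first day the score falls to 4 or lower. That implies the primary analysis uses that date too, and it agrees with 9.3. SAP 8.2, 9.5.1, 10.6.1 and Appendix I and the protocol all point the same way, so a programmer would have to ignore them all to go wrong.

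Much of this stands: the intended endpoint is clear, and the timing sentence supports the row's date for patients who do not lapse (case 7). It does not rescue the row. Plain date arithmetic would need no persistence rule, yet the row sets one. Two neighbouring rows, on symptom resolution and symptom improvement, also carry 24-hour wording, and there it is the real endpoint rule. A reader would naturally take the hypoxia row the same way. The timing sentence also does not say which run counts after a lapse.

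It is also fair to say that the cases were built to differ and imply no rate, and that the run-length wording is a secondary matter.

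**Conclusion.** The point holds. The SAP states two incompatible rules for its primary variable, and the only explicit formula is the wrong one. The word *now* in 9.5.1 suggests that the row survives from an older definition, but that is an inference.

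The documents give no rates of lapse, of death after first improvement or of readmission. The number of patients affected and the direction of any effect on the hazard ratio therefore cannot be derived. The planned 631 events and 780 patients are unaffected. Harm depends on the row being programmed as written, and the loss of same-day discharges depends further on reading 24 hours as two daily scores. This should be fixed before lock, but it does not undermine the design.

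**What to change.** Replace the 9.3 row with wording to this effect: event if (a and c) or (b and c) of Section 10.6.1 is met; time = first day of the qualifying run of scores of 4 or lower − date of randomization + 1; otherwise censored as in Section 10.6.1. Remove the 24-hour wording.

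As a secondary edit, state once how many daily scores make up the run, counting the first, and use that count in SAP 8.2, 9.5.1, 10.6.1 and Appendix I.

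The cost is one table row and one aligned phrase before Stage I database lock. Data collection, sample size and the Cox model do not change.
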